- A protocol outlining regular risk assessments and system audits to ensure a secure transmission of patients' data, including use of encryption protocols such as Secure Socket Layer (SSL) technology. The inclusion of [name] as a co-I on the proposal will ensure that these Privacy and Security guidelines are in accord with norms and existing practices within the clinic.

Protections against Violations of Confidentiality: As part of the process involved in obtaining written informed consent, all patients/PCPs will be reminded that their responses are confidential and that they may refuse to participate in the project or withdraw at any time without explanation, and further, that such an action will in no way affect their future interactions with the FHC and/or FGP. To ensure confidentiality, data will be associated with an individual participant only by an assigned identification number, the code for which will be kept in a locked drawer. Only members of the research team will have access to the participants' personal information file. All computers containing confidential data will meet security requirements established by the HIPAA Security Rules, and established by the Office of Management and Budget (OMB) in OMB Circular No. A-120, Appendix III.

Office of Management and Budget (OMB) in OMB Circular No. A-130, Appendix III - Security of Federal Automated Information Systems. Specifically, all electronic interview data will be saved on a secure server housed by NYULMC and backed up daily or weekly depending upon the receipt of data. PHI will be confined to a secure server that is not connected to the Internet. All computers will be password protected and on a private LAN network. No file and database servers are accessible to the public through the Internet. Prior to inclusion in any data set (internal and external), data will be stripped of all identifying information.

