11.	Communication: 2-item survey assesses the whether the users communication with healthcare provider improved after using tool
12.	Behavior Intention of use: 4-item survey that assesses the likelihood of using the tool within a specific time frame

Description of MJS DIABETES intervention (Phase 2)

Study Number s18-01044

March 17, 2020 - version 9

Phase 2 of the study will not begin until all materials for this phase have been fully developed. These materials will then be submitted to the IRB via a modification for review and approval.

Patient intervention: MJS DIABETES is comprised of 5 components: 1) PRO assessments, sent via text message; 2) adherence text message assessments; 3) data-driven feedback text messages 4) motivational text messages; and 5) journal reports that visually display PRO data.

MJS helps patients (and their provider) see how their diabetes symptoms and psychosocial functioning are changing overtime. Participants who enroll in the study agree to have messages sent to their phone based on one of several PRO categories. These include: (1) diabetes quality of life; (2) overall emotional health; (3) lifestyle behaviors; (4) medication adherence; and (5) physical functioning. PRO questions will be sent on a daily or weekly basis, depending on the PRO (i.e., adherence is a daily measure while quality of life is sent on a weekly basis). The list of potential PROs that will be sent to patients over the course of the 12-month study and their primary questionnaire source are shown in the Table below. No PHI will be collected in the MJS DIABETES tool. All data is a numerical response that is anonymous.

Potential MJS PROs	Scaling	Source
Over the past week, how would you rate your level of fatigue because of your diabetes?	0 (not at all tired)-10 (extremely tired) scale	Global Health PROMIS Tool
How would you rate your sleep quality over the past 7 days?	0 (very poor)-10	NIH PROMIS Sleep

	(excellent) scale	Quality
Over the past week, how often were you able to take your diabetes medication on time?	Never Rarely Sometimes Often Always	Diabetes self-management questionnaire
How many of the last seven days have you followed a healthful eating plan for diabetics?	0-7 days	Summary of Diabetes Self-Care Activities
In general, my present quality of life is	As good as it can be Good Quite good Neither good or bad Quite bad Bad As bad as it could possibly be	Audit of Diabetes Dependent Quality of Life

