Low Compliance Message (always triggered if 3 consecutive days are missed): We haven't heard from you in the last 3 days. Text HELP if you need assistance in the journaling program.

Good Compliance Message: You have answered 10 text messages in a row for the

Good Compliance Message: You have answered 12 text messages in a row for the journaling program. Keep it up!

% Completed Message 1: You have responded to 85% of the messages over the past 4 weeks in the journaling program.

% Completed Message 2: Congratulations! You are halfway through the journaling program.

Mobile Opt-in/Opt out Process: After completing informed consent, patients randomized the intervention condition will meet with the RA to receive training on how to use the intervention and opt in to receive SMS messages. Per carrier policies to opt in, patients must provide their mobile numbers and carrier information. Once their information has been added to the system, they will receive a SMS asking them to reply to confirm their participation. To confirm, patients will need to reply via text message.

This step verifies their mobile number and joins them to the intervention. They will receive a welcome message.

To cancel or opt out of the program at any time, patients will be required to send the word 'STOP' to any program message. This information is communicated to the patient at the time of registration, via a Mobile Terms and Conditions document – which they will be required to sign. The opt out information is also communicated to them within the first program confirmation SMS, as well as once a month, in a SMS message sent as part of their subscription service.

Study Number s18-01044

March 17, 2020 - version 9

All additional carrier compliance terms will also be adhered to. A HELP message, and an invalid response message will be developed. Carrier specific rate information will be included in messages as required.

Patients will then be instructed on how to respond to the SMS messages and asked to demonstrate their ability to understand.

Journal report: After the first week, and every 2 weeks thereafter, patients will receive a journal report that visualizes their responses to the text message questions in straightforward graphs and displays the adherence responses in a calendar. The reports are intended to help patients reflect on changes in their responses overtime, and discuss how their symptoms and functioning have changed in between visit.

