PCPs: The EHR-integrated journal reports will provide PCPs with quantitative assessments of the extent to which patients are adhering to their T2D regimen, the psychosocial factors that may inhibit adequate glycemic control, and the diseases impact on their functional status. Reports of patient PRO data will be uploaded to the EHR every two weeks. Providers will be able to access reports of patients' PRO data via the MJS-EHR interface during visits with the patient or asynchronously to track patients' PROs between visits. Based on our pilot data, we will encourage providers to use the reports to support patient engagement and shared decision-making in the clinic visit, set priorities for the visit, and discuss trends in PRO data as they relate to behavioral and clinical outcomes. Prior to the initiation of the trial,

all participating PCPs will receive standardized training in the MJS-EHR interface functionalities as well as best practices for patient-centered discussions of the data visualizations (Table 6). The ability to receive and review PRO reports between clinic visits may also offer several opportunities to improve patient care such as by: reducing critical information gaps about patients' condition or symptoms; supplementing existing clinical data; providing PCPs with a comprehensive view of patients' ongoing experience of their

Study Number s18-01044

March 17, 2020 - version 9

illness (symptoms, function and well-being); as well as meeting meaningful use requirements for two-way electronic communications.

Description of UC group

Patients randomized to the UC group will receive standard diabetes treatment recommendations as determined by their PCP. Rationale for UC condition: The UC group was designed to mimic usual care as delivered in primary care practices. We believe that including an alternate approach such as an attention control condition would defeat the purpose of this trial, which is to compare the efficacy of an innovative approach to collect and track PROs for diabetes self-care in real-world practice-based settings with particular attention to its integration into standard clinical practice.

Table 6. Treatment Fidelity Strategies

Element	Strategy

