Patient diabetes distress: will be assessed with the well-validated and widely used 17-item Diabetes Distress Scale, which is assessed using a Likert type scale from "1= not a problem" to "6= a very serious problem." For each item patients rated the degree of distress the potential problem a person with diabetes may experience. To score, the sum of all the patient's responses is divided by 17. A mean score of 3 or higher is considered a level of distress that needs medical attention. In the event of an elevated score, a message will be sent to the patient's primary care provider and be noted in the patient's study record.

Patient outcome expectations (motivation): will be assessed with the 20-item Outcome Expectations Questionnaire (adapted from McCaul et al., 1987), which assesses participants' perceptions of the positive and negative consequences of performing diabetes self-care behaviors (e.g., "If I exercise daily, my diabetes will be better controlled"). The measure has been previously validated in a diverse sample of patients with type 2 diabetes, The Cronbach α of the total scale is 0.86.

Patient-provider communication (opportunity): will be assessed with the Interpersonal Processes of Care Survey, a patient-reported, multidimensional instrument designed to assess interpersonal aspects of care. It is validated for patients of diverse racial/ethnic groups and available in Spanish and English. The IPC assesses 7 subdomains of communication, patient-centered decision making, and interpersonal style. As in previous studies, we will also include diabetes-specific communication items related to the fundamental areas of diabetes education including: diet ("how to plan your meals to improve your blood sugar"), foot care ("how to care for your feet"); physical activity ("how to exercise properly"); and other issues ("what is a good number for your blood sugar").

Patient demographic data will include race/ethnicity, place of birth, years in the US, primary language, age, gender, household income, education level, marital status, employment status, health insurance status, smoking and drinking behaviors, and medical comorbidity. PCP demographic data will include gender, race/ethnicity age, years of medical practice,

Study Number s18-01044

March 17, 2020 - version 9

years practicing at the FHC or FGP, and how well they know the patient (range from very well to not at all).

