6.3.2 Informed Consent

Both patients and PCPs will provide informed consent to participate in either phase of this study. The protocol and consent will be approved by the New York University IRB.

Due to COVID-19 and to keep the safety of both our research team and research subjects, we will be collecting consent via telephone. A trained Research Assistant will schedule a time with eligible interested participants to go over the written consent via telephone.

Research Assistants will email or mail a copy of the consent to participants in preparation for the telephone consent. After going over the written consent via telephone, research assistants will also send the consent via a RedCap link where the participant has the opportunity to read the consent and sign electronically, confirming that they read and

Study Number s18-01044

March 17, 2020 - version 9

understood the consent. Research Assistants will also document on RedCap the time and date of the telephone consent and note that the consent process was done via telephone due to COVID-19.

PCPs: A trained RA will meet with PCPs that express interest to provide a fuller description of the study. During this meeting, the PCP will be given a fuller description of the study in clear, easy to-understand language, emphasizing the points made during the letter/telephone/email invitation. All PCPs will be told that their responses are anonymous and confidential, that they may refuse to participate in the project or withdraw at any time without explanation and further, that such action will in no way affect their relationship with the primary care practice. If the PCP remains interested in participating, the RA will provide a copy of the consent form for him/her to read. PCPs will be asked to repeat back the salient points of the consent form to make sure that they understand the study they are agreeing to participate in. If the healthcare provider desires to participate, s/he will sign, and the RA will co-sign. PCPs will receive a copy of the signed informed consent. A second copy will be stored in a secure, locked filing cabinet in a dedicated room.

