Patients: For phase 1 of the study, patient initial verbal consent will be conducted during a telephone call with a RA. During the telephone call the RA will give a fuller description of the study to the participant in clear, easy to-understand language, emphasizing the points made during the initial telephone call/letter/Epic invitation. All patients will be told that their responses are anonymous and confidential, that they may refuse to participate in the project

responses are anonymous and confidential, that they may refuse to participate in the project or withdraw at any time without explanation, and further, that such action will in no way affect their future interactions with their PCP. If the patient remains interested in participating, they will have the option to either complete the focus group in-person in a dedicated room or via a remote session using NYU's secure Webex conferencing platform. For patients opting to complete the focus group remotely, the RA will send a copy of the informed consent to them for signature and include a pre-stamped envelope with return address. The RA will also include a letter with their contact information so the patient can contact the RA to ask for help in reading the consent form. Patients will be asked to mail back their signed consent to the study team before their scheduled focus group. Once the informed consent is received by the RA, the RA will sign and mail a copy to the patient. The original consent will be stored in a secure, locked filing cabinet in a dedicated room.

For Phase 2 of the study, patient consent will be conducted during an in-person meeting with a RA in a private space at the FHC or FGP. During the meeting the RA will give a fuller description of the study to the participant in clear, easy to-understand language, emphasizing the points made during the initial telephone call/letter/Epic invitation. All patients will be told that their responses are anonymous and confidential, that they may refuse to participate in the project or withdraw at any time without explanation, and further, that such action will in no way affect their future interactions with their PCP. If the patient remains interested in participating, they will be provided with a copy of the consent form to read; if the patient asks for help, or evidences a problem in reading the consent due to literacy issues, the RA will read and explain the consent to him/her. Patients will be asked to

Study Number s18-01044

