7.3 Subject Confidentiality

As part of the process involved in obtaining written informed consent, all patients/PCPs will be reminded that their responses are confidential and that they may refuse to participate in

Study Number s18-01044

March 17, 2020 - version 9

the project or withdraw at any time without explanation, and further, that such an action will in no way affect their future interactions with the FHC or FGP. To ensure confidentiality, data will be associated with an individual participant only by an assigned identification number, the code for which will be kept in a locked drawer. Only members of the research team will have access to the participants' personal information file. All computers containing confidential data will meet security requirements established by the HIPAA Security Rules, and established by the Office of Management and Budget (OMB) in OMB Circular No. A-130, Appendix III - Security of Federal Automated Information Systems. Specifically, all electronic interview data will be saved on a secure server housed by NYULMC and backed up daily or weekly depending upon the receipt of data. PHI will be confined to a secure server that is not connected to the Internet. All computers will be password protected and on a private LAN network. No file and database servers are accessible to the public through the Internet. Prior to inclusion in any data set (internal and external), data will be stripped of all identifying information.

Since text messages will be transmitted in this study, a variety of measures will be used to reduce information security risk. Patients' text responses will be securely handled via Rip Road's HIPAA compliant hardware infrastructure. Rip Road follows a set of well-developed policies and procedures vetted by top healthcare organizations in the management and protection of all data tracked through MJS. Patient information will be de-identified for administrative views and for analysis within the Rip Road system. Text messages will not identify patients as having a specific disease or include any PHI such as patients' name.

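### Section 6.3.2 has patients and PCPs told that their responses are anonymous, but the protocol's own data handling makes them coded and, for some Phase 2 answers, visible or notifiable to the patient's PCP

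*Combined protocol and SAP*

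**What the plan says.** Section 6.3.2 sets out what the research assistant tells people at consent. For patients it reads "All patients will be told that their responses are anonymous and confidential", once for Phase 1 and again for Phase 2. For providers it reads "All PCPs will be told that their responses are anonymous and confidential".

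Section 6.1.1, describing the MJS tool, says of the text data: "All data is a numerical response that is anonymous".

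Elsewhere the protocol describes how responses are handled:

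- Sections 3.3.2 and 7.3, covering patients and PCPs: "data will be associated with an individual participant only by an assigned identification number, the code for which will be kept in a locked drawer".
- Section 6.1.1, on opting in to the texting programme: "patients must provide their mobile numbers and carrier information".
- Section 6.1.1, on the PCP side of the intervention: "Reports of patient PRO data will be uploaded to the EHR every two weeks".
- Section 6.1.3, on the Diabetes Distress Scale: "In the event of an elevated score, a message will be sent to the patient's primary care provider".

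**The concern.** Anonymous, coded and confidential are three different promises. Anonymous means that nobody can tie an answer to a person. Coded means that someone holds a key that can. Confidential means that the tie exists but access is restricted. Section 6.3.2 makes the first promise, while the design runs on the other two and, for some answers, shares them with the patient's own provider by intention.

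What is at stake is the accuracy of what people are told before they agree. The text questions ask about missed medication, diet, mood and coping, and the distress scale covers similar ground. Whether one's own PCP sees such answers, or is alerted because of them, matters to the decision to take part and to what one chooses to disclose. Section 6.3.2 wants the explanation in plain language and provides for patients who have trouble reading the form, so the spoken wording carries real weight.

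**Working it through.** There is no figure to reproduce. The check sets the assurance beside the data flow, one group at a time.

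1. **Everyone, both phases.** Sections 3.3.2 and 7.3 attach an ID number to each patient's and PCP's data and keep the code. Section 7.5.1 confirms that IDs can be related back to names using secured information. Section 7.5.1.1 allows identifiers needed for analysis, such as date of birth, into the data set. Data with a retained key are coded, so the assurance fails for all participants on this ground alone.

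2. **Phase 2 patients in the MJS arm.** Opting in requires a mobile number. Reports of the text answers go to the EHR every two weeks, and section 6.1.1 lets the PCP open them at visits and between visits. A report can reach the right chart only if the answers are matched to the patient. Showing a patient's answers to that patient's provider is a component of the intervention (5.1, 6.1.1), so these answers cannot be anonymous, and the sentence in 6.1.1 that calls them so conflicts with the same section.

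3. **Phase 2 patients in either arm.** Section 6.1.3 treats a mean distress score of 3 or more as needing medical attention. An elevated score prompts a message to the patient's PCP and a note in the study record. Table 7 lists the scale with the theoretical mediators, not the process measures, and section 7.5.1 says that all but the process measures are the same in both arms. Usual-care patients are therefore covered too. Identifying the right PCP requires identifying the patient.

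4. **The protocol's other account of consent.** Sections 3.3.2 and 7.3, describing the written consent process, have participants reminded that responses are confidential and do not add anonymous. Section 6.3.2 is the one that departs.

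5. **Reach, at the planned numbers in 5.3.1.** Formative-phase participants are excluded from the trial, so the groups do not overlap.
   - Patients given the assurance: 36 + 282 = 318.
   - PCPs given the assurance: 14 + 14 = 28.
   - Patients whose text answers go to the EHR, at 1:1 allocation: 282 / 2 = 141.
   - Patients subject to the distress message: up to 282. The documents give no expected rate of elevated scores, so the number of messages cannot be estimated.

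**The case against.** The strongest reply is that anonymous is loose usage for coded, and that participants will learn the facts by other routes. Section 6.3.2 requires a fuller description of the study, a written form and a repeat-back of its main points. MJS patients also sign mobile terms, receive one-to-one training and get a handout on the journal report (6.1.1, Table 6). Phase 2 materials go to the IRB before that phase begins. Sections 3.3.2 and 7.3 add that text data are stored without identifiers and that data sets are stripped of identifying information. The sentence in 6.1.1 describes the tool and is not itself something said to patients.

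Much of this stands, and it limits what can be concluded. A reader might infer that patients enrol unaware that their PCP will see their answers. The documents do not show that: the consent form is not among the pages available, and it may disclose both the EHR upload and the distress message.

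A reader might also infer a one-arm bias, with candour or withdrawal shifting once MJS patients realise who reads their texts. That is speculative. The self-care and mediator questionnaires are separate from the text answers, and no section uploads them to the EHR. The one stated disclosure from them, the distress message, applies in both arms. Any change in candour because PCPs see the texts belongs to the intervention and would remain after rewording.

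The reply does not rescue the word itself. Storage without identifiers does not help when the answers must be matched to a chart. Stripping of data sets sits awkwardly with section 7.5.1.1, which lets date of birth in. An accurate form would still be contradicted by the assurance spoken alongside it.

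**Conclusion.** The contradiction is established. As written, section 6.3.2 instructs staff to tell all participants something that the protocol's data handling makes untrue, and section 6.1.1 misdescribes the MJS data in the same way. The conclusion rests on the ordinary meaning of anonymous and, for the usual-care arm, on reading Table 7 together with section 7.5.1.

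The grounds differ in reach. Only the ID coding applies to everyone; the EHR upload applies to the MJS arm, and the distress message to Phase 2 patients.

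Three further inferences should not be drawn. Confidential is not shown to be false; for the MJS and distress data it needs the qualification that the PCP is shown the text reports or is alerted. Section 6.1.3 says that a message goes to the PCP, not that the score does. And counting uploads (52 / 2 = 26 per MJS patient over 52 weeks) measures reports, not people misled.

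No effect on the primary outcome is claimed, since HbA1c comes from the EHR or a scheduled laboratory test (6.1.3). Power and type I error are untouched. This is a participant-protection correction that should be made.

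**What to change.** - **Section 6.3.2**, for PCPs and for patients in both phases: say that responses are coded and confidential, and remove anonymous.
- **Section 6.1.1**: correct the description of the MJS text data to match.
- **Phase 2 consent script**: add that, for patients assigned to MJS, text answers are displayed to their PCP in the EHR, and that in either arm the PCP is notified of an elevated distress score. This discloses what the protocol already provides for; it does not alter the notification rule.
- **Consent form**: confirm that it says the same, and amend it if it does not.

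The cost is protocol and script wording, submitted as an IRB modification by the route that section 7.9 already describes. No procedure, measure, sample size or analysis changes.
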